All adverse health changes will be assessed for severity by an appropriately qualified member of the MATTS research team, or local clinician. It is their responsibility to review all documentation (e.g. patient records, laboratory and diagnostic reports) related to the event and determine seriousness according to the definitions stated in Table 1.

By definition, major trauma is a life threatening Illness that will result in hospitalisation, disability, or incapacity, and these outcomes will therefore not be classified as SAEs. If an AE is classed as non-serious, these will be recorded by the MATTS research team, and reported on aggregate to CTRU on a monthly basis.

If the AE is classed as serious, an SAE report form must be completed by the MATTS research team and sent to the CTRU within 24 hours of its discovery. The CI will then review causality, and expectedness to determine whether the SAE is related and/or is unexpected. Additional information may be requested from local research team members, research site staff, or GP, at a later date.

Documentation

SAE's deemed unrelated to the triage tool or study procedures will be recorded in the TMF only, and no further action will be taken.

All identified related SAE's will be documented in the participant's source medical records (if relevant) and entered into the study database, and followed up until resolution. A SAE form will be completed for each identified SAE and signed by the Cl. This will be kept in the study

master file and a copy sent to the research site for filing in the investigator site file. If further information is obtained at a later date regarding a SAE, the SAE report form will be updated.

Reporting

Reporting requirements are dependent on the seriousness of the adverse health change and categorisation as expected or unexpected:

- Related expected SAEs, will be reported in aggregate to the PMG, SSC and DMEC prior to each meeting; to the sponsor every 3 months; and to the REC in the Annual Progress Report. Expected SAEs will include: false negative and false positive triage tool results; changes in clinical status during prehospital transportation; expected disease progression (e.g. deteriorating level of consciousness following traumatic brain injury); normal symptoms of underlying injury (e.g. pain, bleeding, nausea); or death and disability from underlying major trauma unrelated to the MATTS triage tool.

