- Unexpected SAEs related to the triage tool or study procedures require expedited reporting. The trial manager will inform the sponsor and relevant NHS R&D department; trauma network and will also inform the REC and DMEC within 15 days of notification using the Health Research Authority (HRA) serious adverse event form.

Figure 3 summarises the safety reporting procedures. SAE data will be reported to the trial governance groups and the Sponsor as aggregated data periodically. This will be monitored at management meetings and, if required, action in regards to safety will be decided. A DMEC will also monitor adverse event data and make recommendations to the Study Steering Committee (SSC) on whether there are any ethical or safety reasons why the study should not continue.

	Definition
Adverse Health Change Terminology*	Definition
Seriousness	
Adverse Event (AE)	An adverse change in health that occurs while a patient is taking part in a study
Serious Adverse Event (SAE)	 Any adverse event occurring while a patient is taking part in a study, that results in: Death Prolongation of Hospitalisation Other significant medical event
Causality	
Unrelated	An adverse change in health that occurs while a patient is taking part in a study which is not caused by or related to study interventions or procedures.
Related	An adverse change in health that occurs while a patient is taking part in a study, which is caused by or related to study interventions. An AE or SAE is considered related if the relationship between the event and trial treatments is:
	 Possible - There is some evidence to suggest a causal relationship. However, the influence of other factors may have contributed to the event (e.g. the participant's clinical condition, other concomitant treatments). Probable - There is evidence to suggest a causal relationship and the influence of other factors is unlikely, or Definite - There is clear evidence to suggest a causal relationship and other possible contributing factors can be ruled out.
Fundada da este	
Expectedness Unexpected	Any adverse health change that is NOT consistent with the known and expected adverse events of trial treatments i.e. it is not listed in the protocol or related documents/literature as an expected occurrence.
Expected	Any adverse health change that IS consistent with the known and expected adverse events of study interventions.
Severity*	
Mild	An adverse health change that does not interfere with routine activities

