The composition of the SSC is detailed in Table 3. The SSC will receive information from the Project Management Group and the DMEC. SSC meetings will be convened by the CI approximately annually. Representatives of the trial sponsor and funder may also be invited to participate. The SSC chairperson will provide advice to the CI, sponsor (University of Sheffield), host institutions (Ambulance services and trauma networks), and funder (NIHR). The SSC will have the power to prematurely close the study if necessary due to safety concerns, futility, or lack of convincing clinical effectiveness.

Table 3. Composition of Study Steering Committee

SSC roles	DMEC roles
Members:	Members:
Independent chair	Independent chair
Lay representative	Independent clinician
Independent statistician	Independent statistician
Independent paramedic	
Independent clinician	
Chief Investigators	

Project Management Group

A Project Management Group (PMG) will oversee day-to-day management of the MATTS validation and service evaluation studies, in accordance with CTRU SOP GOV001. Specific roles will include:

- Ensuring adherence with the study protocol
- Ensuring ethical and GCP standards are met
- Monitoring data quality
- Developing and reviewing paperwork
- Responding to queries from the host institutions

- Developing the study protocol in response to operational challenges
- Review of results
- Dissemination of study findings

The PMG will comprise the CI, study manager, co-investigators, trial statistician, research paramedics, ambulance service Research and Development, paramedic, data manager and lay representatives. The PMG will meet frequently during trial set up and approximately quarterly thereafter.

Data Monitoring and Ethics Committee

An independent DMEC will be organised during the study set up period in accordance with CTRU SOPs. The DMEC will review emerging data and adverse event reports and will ensure that the safety, rights and well-being of study participants are upheld throughout the study. Specific roles will include:

- Approval of the study protocol
- Review and approval of the SAP
- Evaluate interim data
- Review data collection, data linkage, and loss to follow up rates
- Consider emerging evidence from relevant studies
- Advise the SSC on whether there are any ethical or safety reasons why the study should not continue or protocol should be amended
- Advise the SSC on release of interim data

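### Serious adverse events judged unrelated, deaths included, are given two incompatible reporting routes, one of which keeps them from the DMEC

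*Protocol*

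**What the plan says.** All of this is in the Protocol, mainly section 6.1 (Safety reporting).

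- **Definition.** Table 1 makes death a criterion: "Any adverse event occurring while a patient is taking part in a study, that results in: Death". The Management text removes hospitalisation, disability and incapacity from SAE status ("these outcomes will therefore not be classified as SAEs"). It does not remove death.
- **Causality.** SAE forms go to the CTRU within 24 hours. Then "The CI will then review causality, and expectedness to determine whether the SAE is related and/or is unexpected". No independent causality review is described.
- **Documentation.** "SAE's deemed unrelated to the triage tool or study procedures will be recorded in the TMF only, and no further action will be taken". The next paragraph enters related SAEs in the study database and follows them to resolution.
- **Reporting, aggregate.** "Related expected SAEs, will be reported in aggregate to the PMG, SSC and DMEC prior to each meeting". The examples of expected SAEs in this same bullet include false negative and false positive tool results, and also death or disability that comes from the injury and is unrelated to the tool.
- **Reporting, expedited.** "Unexpected SAEs related to the triage tool or study procedures require expedited reporting".
- **Reporting, general.** After the pointer to Figure 3: "SAE data will be reported to the trial governance groups and the Sponsor as aggregated data periodically". Figure 3 itself has two reporting columns, for related SAEs and for unexpected related SAEs.
- **DMEC remit (section 7).** "The DMEC will review emerging data and adverse event reports and will ensure that the safety, rights and well-being of study participants are upheld". Its tasks include evaluating interim data and advising on whether the study should continue. No formal interim analysis is planned.

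**The concern.** The Introduction (section 1) names higher mortality as a possible result of under-triage. A patient harmed in this way dies of the injury, after arriving at a hospital less able to treat it. Case by case, that death looks like any other death from major trauma, and a CI could reasonably call it unrelated. Phase Three is an operational roll-out with no concurrent control group, so there is no comparison arm in which an excess of such deaths would stand out.

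A rule that files unrelated deaths without further action would therefore remove from the DMEC's view the events most likely to carry the signal. The committee that advises on continuing a live triage tool would be relying on attributions already made by one person. Because other sentences point the other way, two people applying the protocol in good faith could send the DMEC quite different reports.

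**Working it through.** The point is about reporting routes, and the protocol states no figure to reproduce. The main check is to follow one event through the text.

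**Step 1. Trace a death in a major trauma patient that the CI judges to be due to the injury and unrelated to the tool.**

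| Text in Protocol section 6.1 | Does this death reach the DMEC? |
|---|---|
| Table 1, SAE definition | It is an SAE |
| Documentation rule for unrelated SAEs | No: filed only |
| Aggregate bullet, by its heading (related and expected) | No |
| Aggregate bullet, by its list of examples | Yes: injury deaths unrelated to the tool are listed |
| Expedited bullet | No |
| Figure 3, both reporting columns | No |
| General sentence on aggregated SAE data | Yes, if read without the limit in Figure 3 |

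Four entries say no and two say yes. The aggregate bullet contradicts itself, because its heading requires relatedness and one of its examples is defined by the absence of it.

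**Step 2. Look for any provision for deaths by tool result or destination.** There is none. The aggregate report would include false negative and false positive results, but a count of false negatives does not show how many of those patients died. The DMEC remit in section 7 speaks generally of emerging and interim data and specifies no table of deaths.

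**Step 3. Illustrate what could be lost.** The protocol gives about 1,200 major trauma cases and a target sensitivity of 95% (section 6.1, Sample size calculation), so expected under-triaged cases = 1,200 × (1 − 0.95) = 60. It gives no mortality rate, so every mortality figure below is an assumption. The flag is the smallest number of deaths r with P(X ≥ r) ≤ 0.025 for X ~ Binomial(60, baseline). The chance of a flag is P(X ≥ r) at the raised mortality.

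| Assumed baseline | Flag at | Mortality doubled | Mortality × 1.5 |
|---|---|---|---|
| 5% | 8 deaths | 0.25 | 0.08 |
| 10% | 12 deaths | 0.55 | 0.18 |
| 15% | 16 deaths | 0.76 | 0.26 |

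Now suppose half of the deaths were filed as unrelated, with mortality doubled from 10% to 20%. The visible rate is 0.5 × 20% = 10%, the same as the baseline. The chance of reaching 12 visible deaths is then about 0.015, which is the false-alarm rate of the rule.

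**The case against.** The strongest reply is that the DMEC is not in fact cut off. The aggregate bullet names unrelated injury deaths and mis-triage results. The general sentence on SAE data carries no limit by relatedness, and section 7 gives the DMEC emerging and interim data. The file-only rule stands under Documentation and not under Reporting, so it may be no more than a filing instruction. An event needs only a possible causal link to count as related. The SOPs cited for safety reporting and DMEC conduct may add more, and they are not reproduced in the protocol.

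Much of this stands. A reader might infer from the file-only rule that the DMEC sees only events already attributed to the tool and cannot detect excess harm among mis-triaged patients. The document does not support that, because some of its sentences send unrelated deaths to the DMEC. Nor does it establish that the CI is judging a tool of the study team's own making: the tool implemented may be an existing one, and any new tool comes from an expert consensus process.

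What does not stand is that the text is adequate as written. The rule forbids further action on unrelated SAEs, which is more than filing. The permissive sentences do not expressly lift it, and the figure that summarises the procedure omits unrelated SAEs.

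The practical limits are also real. Under-triaged patients may differ in case mix from those correctly triaged, so a comparison by tool result is confounded. The DMEC meets about every 6 months and Phase Three lasts 6 months, so timing limits early detection whatever the report contains.

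**Conclusion.** The concern holds as an internal contradiction with a safety consequence. Section 6.1 both withholds from the DMEC and sends to it the deaths that the CI judges unrelated. On the restrictive reading, which the Documentation rule and Figure 3 support, the DMEC would miss deaths attributed to the injury. On neither reading is it given deaths by tool result or destination.

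No sample size, estimate or planned analysis changes. The chance of about 55% that a table of all deaths would flag a doubling rests on 60 under-triaged patients, an assumed baseline mortality of 10%, a one-sided 2.5% rule and a baseline treated as known. Over assumed baselines of 5% to 15% it runs from 0.25 to 0.76. These figures show that full reporting would help and would not guarantee detection. The finding does not depend on them. The amendment should be made before Phase Three starts.

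**What to change.** Reconcile the Documentation and Reporting text of section 6.1 with Figure 3:

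1. In the Documentation rule, strike the word 'only' and the clause on no further action.
2. State that all identified SAEs, whatever their causality, go into the aggregate report to the DMEC, with the CI's causality call shown as a column.
3. In that report, tabulate deaths among linked major trauma cases by tool result and by destination (MTC or non-MTC).
4. Reword the aggregate bullet so that its heading and its examples agree, and add unrelated SAEs to the reporting part of Figure 3.
5. Leave expedited reporting of unexpected related SAEs as it is.

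The table should be confined to linked major trauma cases. Reference-negative patients are not linked to hospital data (section 5.1, carried into Phase Three by section 6.1), so extending it to all of the roughly 150,000 injury calls would need data that the study does not plan to hold. Within that limit the cost is small: a few sentences, an aligned figure and one table, since outcome and destination are already to be collected for these cases. The downside is a longer DMEC report with many injury-related events, and a comparison that case mix confounds, so it can raise a signal but not establish cause.

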Participating ambulance services estimate 150,000 calls for injury per 6 months across the included trauma networks, with TARN data suggesting that approximately 1,200 of these cases represent major trauma (ISS>15). Assuming, based on ASCOT criteria, a triage tool requires sensitivity of 95%, this sample size would provide a 95% confidence interval coverage of ±1.0% for the under-triage rate. Assuming a target specificity of 70% as per

ASCOT guidance, coding 3000 reference standard negative cases (sampling fraction of 2%) would give a 95% confidence interval coverage of $\pm 1.5\%$ for the over-triage rate.

Statistical analyses

The implemented triage tool will be scored using observed data, the presence of a trauma pre-alert recorded, and the actual transport destination collected. Compliance and real life performance of the implemented triage tool will subsequently be assessed. The reference standard will be the MATTS expert consensus definition of trauma with the potential to benefit from MTC care. Under/over-triage, sensitivity, specificity, predictive values, and c-statistics with their 95% confidence intervals (95% CI), will be calculated. The compliance of paramedic transport decisions with triage protocol results will be examined as a proportion with 95% CI. A priori sub-group analyses will examine tool performance in children and the elderly; and in penetrating and urban injury victims.

Safety reporting

In the MATTS Phase Three service evaluation study an optimal candidate triage tool will be voluntarily implemented by participating trauma networks. Adverse changes in the health of patients will be defined, monitored, recorded and reported according to CTRU SOP PM004 and Health Research Authority guidance for non-CTIMP studies. Adverse events (AEs) and serious adverse events (SAEs) related to major trauma triage will be recorded and reported. Table 1 details the definitions used.

Identification

Adverse health changes will be identified by paramedics during implementation of the triage tool and by research paramedics' review of EMS and hospital records. AEs will also be detected through review of ambulance service, hospital and trauma network incident reporting processes. Furthermore local investigators will report any additionally identified adverse health changes.

Management

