DMEC composition (Table 3) and conduct will be in accordance with CTRU SOP GOV003. An initial meeting will be held prior to the start of the trial and then approximately 6 monthly thereafter. No formal interim analyses are planned.

Patient and Public Involvement (PPI)

A public and patient advisory group will be enlisted for collaboration throughout the study. This group will be consulted on all aspects of study conduct, and help with specific tasks such as developing research materials and dissemination. The CI will liaise and mediate between the advisory group and the trial oversight groups, providing support where needed.

8. Publication and dissemination

The study protocol with be registered with an international research registry (ClinicalTrials.gov) and will be made available in the open access University electronic repository. Results of the study will be disseminated in high profile peer-reviewed scientific journals and relevant academic conferences. Authorship will include funded co-applicants, clinical collaborators, research paramedics and the study manager, according to International Committee of Medical Journal Editors (ICMJE) guidelines.

Details of the study, including regularly updated progress reports, will be available on a dedicated study website hosted by the CTRU. Plain English study progress reports will be provided to collaborators, patient advocacy groups, local PPI panels and our service user advisory group. Study developments will also be communicated through social media including twitter. The lay SMG member and service user advisory group will contribute to writing any scientific publications, particularly plain English summaries and conference presentations.

At the end of the study a report will be submitted to the trial funders with full details of study progress and study findings. It is anticipated that this report will be independently peer reviewed and the final accepted report published as a "gold" open access monograph in the *Health Technology Assessment* journal.

9. Finance

The study is funded by the NIHR Health Technology Assessment Programme (grant number 17/16/04). Details have been drawn up in a separate agreement.

10. Ethics approval

Phase 1 sub-studies, and Phase 3 sub studies on acceptability and usability of implemented triage tool do not involve patients and ethical approval will be confirmed with the University of Sheffield.

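### The list of expected SAEs contradicts the protocol's own SAE rules and leaves two reporting routes open for serious harm after a false-negative triage result

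*Protocol*

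**What the plan says.** All of this is in Protocol section 6.1, Safety reporting, unless noted.

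- **Table 1.** An adverse event is an adverse change in health during the study. A serious adverse event is "Any adverse event occurring while a patient is taking part in a study, that results in" death, prolonged hospitalisation or another significant medical event. An event is unexpected if the protocol or related documents do not list it as an expected occurrence.
- **Management.** Adverse health changes are assessed and their seriousness is judged against Table 1. Hospitalisation, disability and incapacity are declared not to be SAEs, because major trauma brings them by definition. Once an event is judged to be serious, the rule is: "an SAE report form must be completed by the MATTS research team and sent to the CTRU within 24 hours of its discovery". Causality and expectedness are reviewed afterwards by the CI.
- **Documentation.** SAEs judged unrelated to the tool or study procedures are filed in the TMF and nothing more is done.
- **Reporting.** Related expected SAEs go in aggregate to the PMG, SSC and DMEC before their meetings, to the sponsor every 3 months and to the REC yearly. This bullet contains the list: "Expected SAEs will include: false negative and false positive triage tool results". The list ends with "death and disability from underlying major trauma unrelated to the MATTS triage tool". Related unexpected SAEs are expedited to bodies including the REC and DMEC within 15 days.
- **Section 7, DMEC.** "An initial meeting will be held prior to the start of the trial and then approximately 6 monthly thereafter". The SSC meets about annually and the PMG about quarterly. Phase Three enrols for 6 months.

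**The concern.** Phase Three is the only part of the programme in which a new tool directs real patients, and under-triage is the main way it could hurt them. The Introduction itself links under-triage to higher mortality. The safety section should therefore leave no doubt about how a serious outcome after a false-negative result is classified and who hears of it, and when.

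The list leaves that doubt. It names tool errors as SAEs although they do not meet the protocol's definition, and it mixes related with unrelated events. It also readmits disability, which another paragraph rules out. Two people applying the text in good faith could send the same death down different routes. Separately, if the list were used as a trigger for forms, the safety system would fill with events in which nobody's health changed, and the few real harms would be harder to see.

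**Working it through.** **1. The list against the other rules**

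| Item in the expected-SAE list | Rule it meets elsewhere in 6.1 | Result |
|---|---|---|
| False positive or false negative tool result | Table 1: adverse change in health with a serious outcome | A wrong result alone meets neither part |
| Death unrelated to the tool | Documentation: unrelated SAEs to the TMF only | Two routes: aggregate reporting, or filed without action |
| Disability | Management: not an SAE | Listed as an SAE and excluded as one |

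**2. A death after a false negative**

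- *Reading A.* The protocol lists the false negative as expected. Table 1 makes expectedness depend on such listing, so the event is related and expected and is reported in aggregate.
- *Reading B.* The only deaths listed are those unrelated to the tool. A death attributed to the false negative is not listed, so it is related and unexpected and is expedited within 15 days.

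The text supports both.

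**3. Timing under Reading A**

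The DMEC interval is about 6 months and enrolment lasts 6 months. No meeting is tied to Phase Three. Meetings exactly 6 months apart would put one inside the window or at its edge, so the next one may coincide with the end of enrolment. An annual SSC meeting can miss the window altogether. The quarterly PMG and the 3-monthly sponsor report would each give about 6/3 = 2 aggregate reports within it.

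**4. How many events the list covers if taken literally**

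The protocol gives no expected SAE count, so there is none to reproduce. Inputs, all from the Phase Three sample size paragraph:

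- "Participating ambulance services estimate 150,000 calls for injury per 6 months across the included trauma networks"
- "approximately 1,200 of these cases represent major trauma (ISS>15"); the negatives are then 150,000 − 1,200 = 148,800
- target sensitivity 95% and target specificity 70%
- 3,000 negatives coded; the stated 2% sampling fraction reproduces as 3,000/150,000 = 2.0%

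Formula: negatives × (1 − specificity) + positives × (1 − sensitivity).

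| Case | False positives | False negatives | Total |
|---|---|---|---|
| Every attended patient, at targets | 148,800 × 0.30 = 44,640 | 1,200 × 0.05 = 60 | 44,700 |
| Coded negatives only, at targets | 3,000 × 0.30 = 900 | 60 | 960 |
| Every attended patient, 66%/88% | 148,800 × 0.12 = 17,856 | 1,200 × 0.34 = 408 | 18,264 |
| Coded negatives only, 66%/88% | 3,000 × 0.12 = 360 | 408 | 768 |

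The 66% sensitivity and 88% specificity are the figures the Introduction cites for an existing tool. Over 182.5 days, 960 is about 5 a day and 44,700 about 245 a day. If only events meeting Table 1 counted, the number could not be computed from the document.

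**The case against.** A reader might infer that the plan commits the team to about 45,000 SAE forms. The documents do not support that. Under Management, seriousness is judged against Table 1 before a form is due, and expectedness is considered only afterwards. On that order a false positive with no health change never reaches the list. The 24-hour clock also runs from discovery, and only 3,000 negatives are coded. The 44,700 is an upper bound that requires every misclassification to be identified and the seriousness step to be skipped.

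A reader might also infer that harm from under-triage reaches independent oversight only after enrolment ends. That too goes beyond the text. Each SAE goes to the CTRU within 24 hours and is reviewed by the CI. The PMG and the sponsor receive aggregates about quarterly, and on Reading B the DMEC hears within 15 days. The DMEC's remit also covers interim data and adverse event reports.

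Finally, the list may be meant to cover expected events whether or not they are related, which would explain the mention of unrelated deaths. Its place inside the bullet on related SAEs makes that hard to sustain, and it would not settle disability or misclassification.

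These points remove the large workload and the claim of a blind DMEC. They do not remove the three contradictions or the choice between Readings A and B. CTRU and sponsor reports do not replace the DMEC's assigned task of advising whether the study should continue.

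**Conclusion.** The expected-SAE list is wrong as written. It conflicts with Table 1 on misclassification, with the Documentation paragraph on unrelated deaths and with the Management paragraph on disability. The important result is that a serious outcome after a false-negative result has two possible classifications, and the route differs between aggregate reporting and a 15-day expedited report.

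Read literally, the list covers about 960 misclassifications through coding and at most 44,700. These counts assume the plan's target accuracy and its 1,200 cases with ISS>15, used here in place of the consensus reference standard. The actual load would be much smaller if the Table 1 step is applied first. The number of serious outcomes after a false negative cannot be derived from the protocol; the 60 expected false negatives are tool errors, not harms.

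This is a patient-safety reporting defect that should be corrected before Phase Three starts. It does not affect the accuracy estimates.

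**What to change.** Reconcile the Reporting list with Table 1 and with the Management and Documentation paragraphs:

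1. Take bare false-positive and false-negative results off the list of related expected SAEs and report them as performance counts.
2. Take events unrelated to the tool, and disability, off the same list, so that each has the single treatment already given elsewhere in the section.
3. State one classification and one reporting route for deaths and other serious outcomes in patients the tool classed negative, and carry it into Figure 3.

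Optionally, time one of the DMEC meetings already planned to fall within Phase Three enrolment, using the SAE data available then. It should not depend on complete false-negative counts. Those need case ascertainment and linkage, and the timetable allows 8 months in Phase Two for collection, linkage and analysis around 4 months of enrolment. For the same reason a fixed review at 3 months with linked counts is hard to justify.

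The cost is a small amendment to the safety section. Timing an existing meeting adds little.
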